4.2 Subject Demographics and Other Baseline Characteristics

4.2.1 Demographic and Baseline Characteristics

Descriptive statistics (number of subjects [n], mean, standard deviation [SD], median, minimum, and maximum for continuous variables and frequency count [n] and percentage [%] of subjects for categorical variables) will be presented for demographic characteristics by study product and overall. These variables include age, sex, race, ethnicity, and stratification group and will be presented for the Safety population (Table 14.1.3.1) and the mITT population (Table 14.1.3.2).

Demographic information will be listed (Listing 16.2.4.1) for all randomized subjects.

4.2.2 General Medical History

Medical and surgical history (in the last year) including allergies or drug sensitivity will be listed in Listing 16.2.4.2, with start date and end date or ongoing at the start of study product.

4.3 Treatments (Study Product, Rescue Medication, other Concomitant Therapies, Compliance)

Randomization details will be listed, including the randomization number, stratification group, the planned study product, the actual study product the subject was randomized to and the randomization date (Listing 16.1.7.1) for all randomized subjects.

4.3.1 Study Product Compliance and Exposure

Compliance data will also be summarized for the mITT population and will be assessed by number of brushings.

Number of actual brushings, brushing compliance (%), number of missed brushings, number of additional brushings will be summarized using descriptive statistics by cumulative visit and by study product (Table 14.2.1).

Number of actual brushings is defined as: [(date of Visit x – date of Visit 2) multiplied by 2 – number of missing brushings + number of additional brushings], where $x = 3, 4, 5, 6$ and 7 , respectively.

Brushing compliance (%) is defined as: $[100 \times (\text{Number of actual brushings} / \text{Expected number of brushings})]$, where expected number of brushings is defined as: [(date of Visit x – date of Visit 2) multiplied by 2].

Study product compliance (number of brushings / brushing compliance [%] / number of missed brushings / numbers of additional brushings) will be listed in Listing 16.2.5.1 for all randomized subjects by study product.

Supervised study product application (subject number, date of visit and time of the supervised procedure) will be listed (Listing 16.2.5.2) for all randomized subjects.

4.3.2 Prior and Concomitant Medication

Prior medications/treatments, including prescription and non-prescription drugs, dietary supplements and herbal remedies, taken in the last 30 days and prior to signing the informed consent form, will be documented in the CRF. The prior and concomitant medications will be coded using a validated medication dictionary, World Health Organization Drug Dictionary (WHODD).

Prior medications and prior non-drug treatments will be listed by subject, with drug name, WHODD Drug Synonym, reason for medication, route, dose, frequency, start date, start day relative to the study product start date, end date and end day relative to the study product start date (Listing 16.2.4.3) for all safety subjects. Prior medications are defined as those which stopped before the first use of the study product.

Concomitant medications and concomitant non-drug therapies taken during treatment will be listed similarly (Listing 16.2.4.4) for all safety subjects with either ongoing or end date

displayed. Concomitant medications are defined as medications that started or stopped on or after the first use of the study product or are ongoing.

Unknown dates will not be imputed. However, if the start or stop date is unknown, then it will be assumed to be concomitant medication unless the partial start date or stop date indicates differently.

4.4 Analysis of Efficacy

The primary population for assessment of efficacy will be the mITT Population.

All p-values presented will be two-sided and assessed at the 5% significance level. A sequential testing strategy will be used to adjust for multiplicity for the comparisons between the Test and Reference Toothpastes in change from Baseline in Schiff sensitivity score and tactile threshold (g) at each assessment time point.

At each timepoint, change from Baseline in tactile threshold (g) will only be assessed for confirmatory evidence if the change from Baseline in Schiff sensitivity score achieves a statistically significant greater reduction for the Test Toothpaste compared to Reference Toothpaste (negative control). This strategy will begin at Day 56, then move to successively earlier timepoints (i.e., Day 56 → Day 28 → Day 14 → Day 7 → Day 3), only moving the next earlier timepoint for confirmatory evidence if all later timepoints achieve statistically significant greater reductions for the Test Toothpaste compared to Reference Toothpaste (negative control) for both Schiff sensitivity score and tactile threshold (g). There will be no further adjustments for multiplicity for the other secondary endpoints (DHEQ-48).

The results from each MMRM will be tabulated, presenting the following information, in addition to the results specified for the primary and secondary analyses below: least square mean change from Baseline for each study product at Days 3, 7, 14, 28 and 56 (based on the observed stratification margins for those MMRM with a term for randomized strata) and used to test for any change from Baseline, with two-sided p-values and 95% CIs.

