9.1.4 Screening Qualifying Tactile Sensitivity

The tactile sensitivity of incisor, canine and pre-molar teeth ([Figure 9-1](#)) exhibiting none of the dentition exclusions, and meeting the EAR, MGI and clinical mobility criteria, will be assessed using a constant pressure probe (Yeaple probe ([Polson, 1980](#))). The probe tip will be placed perpendicular to the facial surface of the tooth and drawn slowly across the exposed dentin to ensure application of the stimulus across the potentially ‘sensitive’ area.

After each application of the tactile stimulus, the subject will be asked to indicate whether they experienced any pain or discomfort. The examiner will tell the subject to only respond ‘yes’ if they feel PAIN or DISCOMFORT when the probe is applied to their tooth. ‘Yes’ and ‘no’ are the only acceptable answers. The subject may respond ‘yes’ if they feel pressure. The examiner will remind them, if needed, that they will feel pressure each time the probe is in contact with the tooth but they should only respond ‘yes’ if they feel pain or discomfort.

The gram setting which elicits two consecutive ‘yes’ responses will be recorded as the tactile threshold (g) for that tooth. At Screening, the upper force setting will be 20g.

Property of Haleon- Confidential

May not be used, divulged, published or otherwise disclosed without the consent of Haleon

- **To be deemed 'eligible' for Baseline DH assessment, a tooth must have a Screening tactile threshold $\leq 20\text{g}$.**
- **If no sensitivity is found at the upper force setting, Screening tactile threshold will be recorded as $> 20\text{g}$ and the tooth will be disqualified from further testing.**

If a subject fails to give a definite answer, the examiner will re-prompt them to provide a response ('yes' or 'no'). If their uncertainty continues, this should be recorded in the source document. If the subject continues to be unsure, or the examiner is unsure of the reliability of their response, the examiner may opt to re-probe at the same force setting (indicated to the scribe by a non-verbal signal, e.g., a hand gesture) or move to the next force setting (10g increase). If the examiner considers the subject's 'yes' response may be between gram settings, a conservative approach should always be adopted, and the lower (more 'severe') tactile threshold (g) recorded.

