9.2.2 Tactile Sensitivity Assessment

Tactile sensitivity will be assessed at Baseline (Visit 2), Day 3 (Visit 3), Day 7 (Visit 4), Day 14 (Visit 5), Day 28 (Visit 6) and Day 56 (Visit 7). The tactile stimulus will be administered, and subject response recorded, as described in [Section 9.1.4](#). The gram setting which elicits the two consecutive 'yes' responses will be recorded as the tactile threshold (g).

- **Baseline:** Assess the tactile sensitivity of all teeth which exhibit none of the dentition exclusions and meet the EAR, MGI and clinical mobility criteria, with a Screening tactile threshold of $\leq 20\text{g}$ and a Screening Schiff sensitivity score ≥ 2 .

The upper force setting will be 20g; if no sensitivity is found at the upper setting, record tactile threshold as $> 20\text{g}$.

- **Days 3, 7, 14, 28 & 56:** Assess the tactile sensitivity of the **two 'Test Teeth' only** (i.e., the two teeth selected by the clinical examiner at Baseline, as described in [Section 8.2.1.6](#)).

The upper force setting will be 80g; if no sensitivity is found at the upper setting, record the tactile threshold as $> 80\text{g}$.

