1.2 Study Objectives

Study objectives and endpoints are defined in [Table 1-2](#):

Table 1-2 Study Objectives and Endpoints

Objectives	Endpoints
Efficacy	
Primary	
To demonstrate the clinical efficacy of a 5% CSPS toothpaste in reducing DH to an evaporative (air) stimulus (as measured by Schiff sensitivity score), compared to a negative control toothpaste, after 8 weeks twice daily use.	Change from Baseline in Schiff sensitivity score at Day 56 (Week 8).
Secondary	
To demonstrate the clinical efficacy of a 5% CSPS toothpaste in reducing DH to a tactile stimulus (as measured by tactile threshold in grams [g]), compared to a negative control toothpaste, after 8 weeks twice daily use.	Change from Baseline in tactile threshold (g) at Day 56 (Week 8).
To investigate the clinical efficacy of a 5% w/w CSPS toothpaste in reducing DH to evaporative (air) and tactile stimuli (as measured by Schiff sensitivity score and tactile threshold (g), respectively), compared to a negative control toothpaste, after 3-, 7-, 14- and 28-days twice daily use.	
Change from Baseline in Schiff sensitivity score at Days 3, 7, 14 & 28.Change from Baseline in tactile threshold (g) at Days 3, 7, 14 & 28.
To describe subject-perceived changes in oral health-related quality of life (OHRQoL), as measured by the Dentin Hypersensitivity Experience Questionnaire (DHEQ-48), after 4- and 8-weeks twice daily use of their assigned investigational toothpaste.	At Day 28 (Week 4) & Day 56 (Week 8): Change from Baseline in DHEQ-48 endpoints. Section 1 
Impact on Everyday Life (Q7-9) Section 2 
Total Score (Q1-34)Individual Domain Scores
Restrictions (Q1-4)Adaptation (Q5-16)Social Impact (Q17-21)Emotional Impact (Q22-29)

Haleon Confidential

CCI

Statistical Analysis Plan Template v6.0

Page 10 of 40

Objectives	Endpoints
Efficacy	
 - Identity (Q30-34) • Global Oral Health Score (Q35) • Effect on Life Overall Score (Q36-39)
Exploratory	
To investigate subject satisfaction with their assigned investigational toothpaste for the overall management of DH, as measured by a Numeric Rating Scale (NRS), after 8 weeks treatment.	At Day 56 (Week 8): Satisfaction NRS score
Safety	
To monitor the safety and oral tolerability of the investigational toothpastes over 8 weeks twice daily use.	Treatment emergent adverse events (TEAEs).

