This study will be considered successful if the 5% CSPS toothpaste demonstrates statistically significant, superior anti-hypersensitivity efficacy, compared to the negative control toothpaste, as measured by Schiff sensitivity score at Day 56 (Week 8).

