4.4.2 Secondary Efficacy Endpoints

4.4.2.1 Change from Baseline in Tactile Threshold (g) at Day 56

The key secondary variable is the change from Baseline in tactile threshold (g) at Day 56.

Tactile threshold (g) will be derived as the mean value for the two ‘Test Teeth’ (selected at Baseline). Change from Baseline will be derived for each individual tooth first before calculating mean change for the two ‘Test Teeth’ where change from Baseline in tactile threshold (g) at Day x is defined as [(tactile threshold at Day x) minus (Baseline tactile threshold)].

Descriptive statistics (n, mean, SD, standard error [SE], median, minimum, and maximum) will be presented for tactile threshold (g) calculated as the average score of the two test teeth at each assessment time point in Table 14.2.3.1.1 for all subjects in mITT population by study product. Raw means (\pm SE) of the tactile threshold (g) at each time point will be plotted by study product in Figure 14.2.2.2.1 for all subjects in mITT population.

Individual tactile threshold (g) data will be listed for each subject by visit and study product group in Listing 16.2.6.3 and Listing 16.2.6.4, for Screening and Baseline, and separately for two test teeth respectively, for all randomized subjects.

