4.4.2.1.1 Statistical Hypothesis, Model and Method of Analysis

The following null and alternative hypotheses will be evaluated:

- H_0 : There is no difference in change from baseline in tactile threshold (g) in the Test Toothpaste compared to Reference Toothpaste
- H_1 : There is a difference in change from baseline in tactile threshold (g) in the Test Toothpaste compared to Reference Toothpaste

Key secondary endpoint, change from Baseline in tactile threshold (g) at Day 56, will be analysed using the same MMRM method detailed in [Section 4.4.1.2](#) but with Baseline tactile threshold (g) as a covariate (rather than Baseline Schiff sensitivity score). In addition, the maximum Baseline Schiff sensitivity score of the two ‘Test Teeth’ (2 or 3) will be fitted as a fixed effect. The results will be presented in Table 14.2.3.2.1.

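### The rule for stepping back from Day 56 asks for a greater reduction in tactile threshold, where benefit is an increase, so read literally a toothpaste that works on both measures stops there

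*SAP*

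**What the plan says.** SAP 4.4 sets a fixed order for the confirmatory tests: Schiff then tactile at Day 56, then the same pair at Days 28, 14, 7 and 3. It has two conditions.

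- Within a visit, tactile threshold is tested for confirmatory evidence only "if the change from Baseline in Schiff sensitivity score achieves a statistically significant greater reduction for the Test Toothpaste". The direction is correct for Schiff.
- To move to the next earlier visit, all later visits must show "statistically significant greater reductions for the Test Toothpaste compared to Reference Toothpaste (negative control) for both Schiff sensitivity score and tactile threshold (g".

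Protocol 12.3 has both conditions in the same wording.

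The tactile scale is described elsewhere. When a response may fall between two force settings, Protocol 9.1.4 wants "the lower (more 'severe') tactile threshold (g) recorded". For the visits after Baseline, Protocol 9.2.2 says "if no sensitivity is found at the upper setting, record the tactile threshold as" greater than 80 g. Under SAP 4.4.2.1, change from Baseline "is defined as [(tactile threshold at Day x) minus (Baseline tactile threshold". The alternative hypothesis in SAP 4.4.2.1.1 has no direction: "There is a difference in change from baseline in tactile threshold (g) in the Test Toothpaste compared to Reference Toothpaste".

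**The concern.** One word, reduction, is applied to two scales that run in opposite directions. Schiff goes from 0 (no response) to 3 (painful), so a fall is benefit. Tactile threshold is the force that provokes pain, so a fall is worsening. As worded, the second condition asks the Test Toothpaste to be significantly better on air sensitivity and significantly worse on tactile sensitivity before an earlier visit can be tested.

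This sentence is the decision rule of the multiplicity procedure. There are 5 visits x 2 measures = 10 ordered tests, and it controls all but the two at Day 56, so eight. Among them is the Day 3 Schiff comparison on which SAP 1.4 bases the sample size, and with it the question of how soon relief begins. If the wording is corrected only after unblinding, the correction can be attacked as a post hoc change to the testing rule.

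**Working it through.** **1. Direction of each measure.** Write D for Test minus Reference in mean change from Baseline (visit value minus Baseline).

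| Measure | Worst end | Best end | Benefit | Condition as written |
|---|---|---|---|---|
| Schiff score | 3 | 0 | D < 0 | D significantly < 0 |
| Tactile threshold (g) | low grams | above 80 g | D > 0 | D significantly < 0 |

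The tactile row contradicts itself: a significant tactile benefit fails the condition by definition. This takes the more permissive literal reading, a between-group difference. If an actual fall from Baseline were also required there would be little room for it, because test teeth enter at 20 g or less and the lowest calibrated setting in Protocol 9.1.4 is 10 g.

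**2. The plan's own sample size.** Inputs from SAP 1.4: difference 0.25, SD 0.55, 105 per group, two-sided 5%.

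- Standardized effect: 0.25/0.55 = 0.4545.
- Mean of the test statistic: 0.4545 x sqrt(105/2) = 0.4545 x 7.246 = 3.293.
- Power by t-test: 0.906 (103 per group is the smallest number reaching 90%).
- Dropout: 105/0.90 = 116.7, so 117 per group.

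The stated 90% power, 105 and 117 are reproduced.

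**3. Chance of meeting the condition at Day 56.** The documents give no tactile effect or SD, so the following are assumptions: a true tactile benefit d of 0.2 to 0.6 SD; the Schiff effect of 0.4545 SD, which is the Day 3 planning value; 105 per group; and a correlation r of 0 to 0.8 between the two statistics when both are signed so that benefit is positive. The statistics are taken as bivariate normal with critical value 1.96. For r = 0:

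- As written: Φ(3.293 − 1.96) x Φ(−1.96 − 7.246d)
- Corrected: Φ(3.293 − 1.96) x Φ(7.246d − 1.96)

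with Φ(1.333) = 0.909. At d = 0.2 these are 0.909 x Φ(−3.409) = 0.909 x 0.00033 = 0.0003 and 0.909 x Φ(−0.511) = 0.909 x 0.305 = 0.277.

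| d (SD) | As written, r = 0 to 0.8 | Corrected, r = 0 to 0.8 |
|---|---|---|
| 0.2 | 3.0e-4 to 1.7e-6 | 0.277 to 0.305 |
| 0.3 | 1.6e-5 to 4e-9 | 0.531 to 0.582 |
| 0.4 | at most 5.4e-7 | 0.751 to 0.805 |
| 0.6 | at most 1.3e-10 | 0.901 to 0.908 |

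If the Day 56 Schiff test were certain to succeed, only the tactile factor remains: at most 0.00033 as written, and 0.305 to 0.992 corrected.

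**4. Could the literal rule let a harmful paste through?** With harm of 0.4545 SD on both measures the chance is at most Φ(−5.253) x Φ(1.333) = 7.5e-8 x 0.909 = 6.8e-8, because a significant Schiff reduction is still needed. With no Schiff effect and tactile worsening of 0.2 to 0.6 SD it is at most 0.025. Only the planned Schiff benefit combined with tactile worsening of that size gives a sizeable chance, 0.22 to 0.90.

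**The case against.** The strongest reply is that the sentence speaks of reductions for the two measures, not in them, and can be read as reductions in dentin hypersensitivity. SAP 1.2 uses that language: "To demonstrate the clinical efficacy of a 5% CSPS toothpaste in reducing DH to a tactile stimulus". A plan that caps Baseline at 20 g and raises the ceiling to 80 g afterwards is clearly built to capture rises, and no sensible analyst would require a fall. On this view the probabilities only restate that a wrong-sign condition fails, and they borrow a Day 3 Schiff effect although the plan expects the effect to grow.

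Much of this stands. Improvement on both measures is the likely intent, and the near-zero figures follow from the sign alone. A larger Day 56 Schiff effect would move the corrected range towards the one shown with Schiff certain.

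It does not repair the rule. The sentence names the two measured variables. The sentence just before it uses reduction for the change in Schiff score itself, the tactile hypothesis has no direction, and neither document says that an increase in tactile threshold is the criterion. A confirmatory rule should not depend on the analyst setting its words aside.

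**Conclusion.** The concern holds: the condition is wrong as written in both documents. Applied literally, it ends confirmatory testing after Day 56 in the very case where the toothpaste works on both stimuli. The size of the loss on that reading rests on the assumed tactile effects and correlations, but the direction error does not depend on them.

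The reach is limited. Study success is judged "as measured by Schiff sensitivity score at Day 56 (Week 8" and is untouched. The Day 56 tactile test is opened by Schiff alone. Estimates, confidence intervals and p-values are still reported at every visit. Only the confirmatory status of the earlier visits is at stake. This is a wording error rather than a design flaw, but it should be fixed before unblinding.

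**What to change.** In SAP 4.4 and Protocol 12.3, state the direction separately for each measure. For example: testing proceeds to the next earlier visit only if, at every later visit, the Test Toothpaste shows both a significantly greater reduction in Schiff score and a significantly greater increase in tactile threshold (g) than the Reference Toothpaste.

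The cost is one sentence in each document, made before unblinding. No extra data or subjects are needed, and the sample size and significance level stay as they are. SAP section 5 currently declares no changes from protocol version 2.0, so it should record the correction.

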4.4.1 Primary Efficacy Endpoint

4.4.1.1 Change from Baseline in Schiff Sensitivity Score at Day 56

The primary efficacy variable is the change from Baseline in Schiff sensitivity score at Day 56.

Schiff sensitivity score will be derived as the mean score for the two 'Test Teeth' (selected at Baseline). Change from Baseline will be derived for each individual tooth first before calculating mean change for the two 'Test Teeth' where change from Baseline in Schiff sensitivity score at Day x is defined as [(Schiff sensitivity score at Day x) minus (Baseline Schiff sensitivity score)].

Descriptive statistics (n, mean, SD, standard error [SE], median, minimum, and maximum) will be presented for Schiff sensitivity score calculated as the average score of the two test teeth at

each assessment time point in Table 14.2.2.1.1 for all subjects in mITT population by study product. Raw means (\pm SE) of the Schiff sensitivity score at each time point will be plotted by study product in Figure 14.2.2.1.1 for all subjects in mITT population.

Individual Schiff sensitivity score data will be listed for each subject by visit and study product group in Listing 16.2.6.1 and Listing 16.2.6.2, for Screening and Baseline, and separately for two test teeth respectively, for all randomized subjects.

4.4.1.2 Statistical Hypothesis, Model, and Method of Analysis

The following null and alternative hypotheses will be evaluated:

- H_0 : There is no difference in change from baseline in Schiff sensitivity score in the Test Toothpaste compared to Reference Toothpaste
- H_1 : There is a difference in change from baseline in Schiff sensitivity score in the Test Toothpaste compared to Reference Toothpaste

Change from Baseline in Schiff sensitivity score at Day 56 will be analysed using a MMRM with study product, visit and [study product x visit] interaction as fixed effects, and Baseline Schiff sensitivity score as a covariate. Note that since the Baseline Schiff sensitivity score will be included as a covariate, the Baseline Schiff stratification value will not be included in the model. Subject will be included as a repeated measure with unstructured covariance matrix. Kenward-Roger's degrees of freedom approach will be applied (Kenward, 1997). The difference between the least square mean changes from Baseline for the Test Toothpaste compared to Reference Toothpaste (negative control) at Day 56 from the MMRM will be presented, along with the two-sided p-value and 95% CIs. In the event that the model does not converge on the unstructured covariance matrix, an appropriate alternative will be considered.

Using the above model, the adjusted mean change from baseline in the Schiff sensitivity score will be reported by study product along with 95% confidence intervals (CIs) and p-values testing for a non-zero change from baseline and will be provided in Table 14.2.2.2.1. Also, mean differences between Test Toothpaste compared to the Reference Toothpaste in the change from baseline in Schiff sensitivity score at Day 56 will be presented along with 95% CIs and p-values in the same Table 14.2.2.2.1.

The assumptions of normality and homogeneity of variance in the MMRM will be investigated. In case of violation of these assumptions, a suitable non-parametric test (Van Elteren Test, adjusted for the randomization stratification, Maximum Baseline Schiff sensitivity score) will be performed to assess the change from Baseline comparison (Test Toothpaste vs. Reference Toothpaste at Day 56); the results will be provided to support the MMRM results.

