12.3.1 Primary Endpoint Analysis

The primary endpoint of this study is the change from Baseline in Schiff sensitivity score at Day 56 (Week 8); the primary hypothesis test will be the comparison between the Test Toothpaste and the Reference Toothpaste (negative control) in the mITT population.

Schiff sensitivity score will be derived as the mean score for the two 'Test Teeth' (selected at Baseline). Change from Baseline will be derived for each individual tooth first before calculating mean change for the two 'Test Teeth' where change from Baseline in Schiff sensitivity score at Day X is defined as [(Schiff sensitivity score at Day X) minus (Baseline Schiff sensitivity score)].

Change from Baseline in Schiff sensitivity score at Day 56 will be analysed using a MMRM with investigational product, visit and [investigational product x visit] interaction as fixed effects, and Baseline Schiff sensitivity score as a covariate. Subject will be included as a repeated measure with unstructured covariance matrix. Kenward-Rogers degrees of freedom approach will be applied ([Kenward, 1997](#)). The difference between the least square mean changes from Baseline for the Test Toothpaste compared to Reference Toothpaste (negative control) at Day 56 from the MMRM will be presented, along with the two-sided p-value and 95% CIs.

The assumptions of normality and homogeneity of variance in the MMRM will be investigated. In case of violation of these assumptions, a suitable non-parametric test (adjusted for the randomization stratification) will be performed to assess the change from Baseline comparison (Test Toothpaste vs. Reference Toothpaste at Day 56); the results will be provided to support the MMRM results.

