1.4 Sample Size Calculation

Sufficient subjects will be screened and entered into the acclimatization period to randomize approximately 234 subjects to study product (approximately 117 subjects per treatment group) to ensure approximately 210 complete the study (approximately 105 subjects per treatment group), allowing for approximately 10% dropouts.

The study will be sufficiently powered to demonstrate statistical superiority of the Test Toothpaste compared to the Reference Toothpaste (negative control) for the change from Baseline in the Schiff sensitivity score after 56 days, i.e., 8 weeks, (primary objective) and 3 days (key secondary objective, earliest time point) treatment. It is anticipated that the treatment effect will increase over time. A sample size of 105 evaluable subjects per treatment group will provide 90% power to detect a mean difference of 0.25 units (SD = 0.55) in change from Baseline in Schiff sensitivity score after 3 days treatment, using a 2-tailed 2-sample t-test with a 5% significance level. The sample size calculation was performed using PASS software version 23.0.1.

The dropout rate and SD estimates are based on the results of DH efficacy studies of similar design and duration (Clinical Studies CCI [REDACTED] and CCI [REDACTED] sponsor data held on file, available on request).

2 Planned Analyses

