4.4.2.4.1 Statistical Hypothesis, Model and Method of Analysis

The following null and alternative hypotheses will be evaluated:

- H_0 : There is no difference between baseline and post-baseline (Day 28, Day 56)
- H_1 : There is a difference between baseline and post-baseline (Day 28, Day 56)

Change from Baseline for each DHEQ endpoint listed above will be analyzed using a MMRM with visit and stratification [maximum Baseline Schiff sensitivity score of the two 'Test Teeth' (2 or 3)] as fixed effects, and the respective Baseline DHEQ score as a covariate. Subject will be included as a repeated measure with unstructured covariance matrix. Kenward-Roger's degrees of freedom will be applied. The estimates of the adjusted mean (SE) change from Baseline will be presented along with 95% CIs for each treatment group. In the event that the model does not converge on the unstructured covariance matrix, an appropriate alternative will be considered.

Using the above model, the adjusted mean change from baseline in each DHEQ endpoint listed above will be reported by study product group along with 95% CIs and p-values testing for a non-zero change from baseline will be provided in Table 14.2.4.2.1 and 14.2.5.1-8.2.1, for Section 1 and Section 2 respectively.

The assumptions of normality and homogeneity of variance in the MMRM will be investigated. In case of violation of these assumptions, a suitable non-parametric test (Wilcoxon Signed Rank Test) will be performed to assess the change from Baseline comparison (Post-Baseline vs. Baseline); the results will be provided to support the MMRM results.

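### The Schiff and tactile MMRMs impose one linear Baseline slope on all five visits; a Baseline-by-visit term would lift that unneeded assumption at almost no cost

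*SAP*

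**What the plan says.** The primary model in SAP 4.4.1.2 is an MMRM "with study product, visit and [study product x visit] interaction as fixed effects, and Baseline Schiff sensitivity score as a covariate". Protocol 12.3.1 has the same form: "interaction as fixed effects, and Baseline Schiff sensitivity score as a covariate". The within-subject covariance is free: "Subject will be included as a repeated measure with unstructured covariance matrix". The randomization stratum is left out on purpose because Baseline Schiff is already a covariate: "the Baseline Schiff stratification value will not be included in the model".

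The tactile model (SAP 4.4.2.1.1; protocol 12.3.2) repeats this structure, "but with Baseline tactile threshold (g) as a covariate (rather than Baseline Schiff sensitivity score", and adds the stratum as a fixed effect. Both models span five post-Baseline visits; SAP 4.4 asks for the "least square mean change from Baseline for each study product at Days 3, 7, 14, 28 and 56".

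Neither document includes a Baseline-by-visit term, gives a reason for equal slopes or plans a check of them. The only assumptions to be investigated are normality and homogeneity of variance. The DHEQ models also have a single Baseline term ("as fixed effects, and the respective Baseline DHEQ score as a covariate"), but over two visits, Days 28 and 56.

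**The concern.** For a change score, the slope on Baseline equals the slope of the later score on Baseline, minus 1. If later scores follow Baseline less closely as time passes, the slope for change moves towards -1. Protocol 4.2 describes dentin hypersensitivity as episodic and names regression to the mean as a risk, so some drift between Day 3 and Day 56 is plausible. Neither document shows that it occurs.

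If it does, the pooled slope is wrong at the first and last visits, and Day 56 is the primary time point. Two things are at stake. Baseline variation that the model could explain stays in the Day 56 residual and widens the reported standard error. In addition, the missing-data argument (protocol 12.3.7; SAP 4.4.4) relies on subjects being alike given their Baseline and other results, which needs the mean to be modelled correctly in Baseline.

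**Working it through.** **1. The plan's own figure.** SAP 1.4 gives a difference of 0.25, SD 0.55, 90% power, and a comparison "using a 2-tailed 2-sample t-test with a 5% significance level". The normal approximation is n = 2(1.960 + 1.282)² × 0.55² / 0.25² = 101.7, so 102 per arm. With the t distribution, 103 per arm gives 90.1% power and 105 gives 90.6%. Allowing for dropout, 105 / 0.90 = 116.7, so 117 per arm and 234 in total. The stated figure reproduces. It rests on an unadjusted t-test, so the Baseline slope does not enter it.

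**2. Cost of the term.** One slope becomes five, which is 4 more parameters. The t critical value moves from 1.9714 to 1.9717.

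**3. Approximate size.** Let δ be the true Day 56 slope minus the pooled slope. With complete data, the model-based standard error is inflated by √(1 + σ_B²δ²/σ²), where σ_B is the Baseline SD and σ the Day 56 residual SD. Each Test Tooth scores 2 or 3 at Baseline (protocol 5.2), so the subject mean is 2, 2.5 or 3 and its SD is at most 0.5. I assume σ_B = 0.40 and σ = 0.5. With equal visit SDs and evenly spaced slopes, the pooled slope is the midpoint.

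- Drift -0.2 to -0.6: δ = -0.2; √(1 + 0.16 × 0.04 / 0.25) = √1.0256 = 1.013, or 1.3% too wide.
- Drift 0 to -1 (extreme): δ = -0.5; √(1 + 0.16 × 0.25 / 0.25) = √1.16 = 1.077, or 7.7% too wide.
- Total drift of 0.2 (δ = -0.1): √1.0064, or 0.3%. Total drift of 0.6 (δ = -0.3): √1.0576, or 2.8%.
- If residual SD also grows from 0.4 to 0.6 over the visits, the pooled slope is pulled towards the early visits. Drifts of 0.2 to 0.6 then give about 0.4% to 9%, depending on the correlation.

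**4. Simulation.** There were 2000 trials per scenario, each with 234 subjects, five visits, about 10% monotone dropout unrelated to Baseline, stratified blocks of 4, residual SD 0.5, AR(0.6) correlation and a Day 56 difference of 0.25. Fits approximated REML and were not exact Kenward-Roger. Each cell is common slope / by-visit slope.

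| Assumed slopes, Day 3 to Day 56 | Model SE | Empirical SE | Power | Type I error |
|---|---|---|---|---|
| Equal, -0.4 | 0.0685 / 0.0686 | 0.0696 / 0.0696 | 94.6% / 94.6% | 4.1% / 4.1% |
| -0.2 to -0.6 | 0.0694 / 0.0685 | 0.0697 / 0.0698 | 94.2% / 94.3% | 4.1% / 4.3% |
| 0 to -1 | 0.0743 / 0.0685 | 0.0703 / 0.0690 | 93.6% / 95.5% | 4.0% / 5.1% |

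The ratios of model SE are 0.0686 / 0.0685 = 1.001, 0.0694 / 0.0685 = 1.013 and 0.0743 / 0.0685 = 1.085. Bias at Day 56 stayed within 0.003 in every row. Under moderate drift the true scatter of the two estimates is the same to within simulation error, so the gain is a narrower reported SE and hardly any reduction in actual variability.

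**5. Chance imbalance.** Stratification cut the SD of the between-arm Baseline difference from about 0.052 to 0.025. Even a slope misfit of 0.3 then moves the estimate by about 0.3 × 0.025 = 0.0075, which is 3% of 0.25, in either direction.

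**6. Dropout related to arm and Baseline.** Dropout was set at 35% in high-Baseline Reference subjects and 6% otherwise (assumed). The common slope then biased the Day 56 difference by about -0.008 under moderate drift and -0.02 under extreme drift, in favour of the Test Toothpaste. Type I error was still 4.8% and 4.4%. The by-visit term brought the bias to within 0.003 of zero.

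Monte Carlo error is about 0.0016 on bias and 1 point on rejection rates.

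**The case against.** The planned model is complete, pre-specified and defensible. With dropout unrelated to Baseline it is unbiased and, if anything, conservative. Under moderate drift the power difference is 0.1 point, within simulation error. The 0.25 used for Day 56 is the Day 3 design value; SAP 1.4 expects a larger effect later, which would shrink any power difference further. Bias needed a strongly unequal dropout pattern that nothing in the documents predicts. All of this stands, and it keeps the point minor.

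Several stronger readings are tempting, and the documents do not support them.

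- A reader might infer that because the treatment effect is expected to grow, the Baseline slope must steepen. It need not: a between-arm difference can grow at an unchanged slope.
- A reader might see the missing stratum in the primary model as a fault. SAP 4.4.1.2 gives the reason, and the tactile and DHEQ models carry the stratum because they lack Baseline Schiff as covariate.
- A reader might take the added term as free and as curing all misfit. It costs four parameters and addresses only unequal linear slopes, not curvature or the 0 to 3 bounds of the scale.
- Fitting Baseline Schiff as a three-level class by visit would add nine parameters and was not evaluated.

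What the objection does not supply is a reason to assume equal slopes when the model can estimate them from data already collected.

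**Conclusion.** The point holds as a low-cost refinement and does not threaten the primary test. The Schiff and tactile models carry an equal-slope assumption that the plan neither explains nor needs. In the primary model that single slope is the only Baseline adjustment.

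If slopes drift moderately, the reported Day 56 standard error is about 1% too wide. It is nearer 8% under extreme drift, and growing variance can also raise it. The small bias arises only if slopes drift and dropout depends jointly on arm and Baseline.

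These sizes rest on assumed slopes, Baseline SD, residual SD and correlation, none of which the documents give by visit. Only the Schiff model was simulated. For the tactile model the structural argument is the same but its size was not calculated. A reader might extend the point to the DHEQ models in full; with only two post-Baseline visits and a descriptive objective, they have much less reason to change.

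**What to change.** Before unblinding, add [Baseline Schiff sensitivity score x visit] as a fixed effect in SAP 4.4.1.2 and [Baseline tactile threshold x visit] in SAP 4.4.2.1.1. Record both in SAP Section 5, which now reports no departures from the protocol analysis. The models for the earlier visits (SAP 4.4.2.2.1 and 4.4.2.3.1) refer back to these sections and follow automatically.

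The cost is one term and four parameters per model, about 0.1% in the Schiff Day 56 standard error if the slopes prove equal, with no new data, subjects or visits. Adding the matching term to the DHEQ models is optional, for consistency only.
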